1.9 General Considerations

The study is being conducted in compliance with the policies described in the DRCR.net Policies document, with the ethical principles that have their origin in the Declaration of Helsinki, with the protocol described herein, and in accordance with ICH E6 Good Clinical Practice. All study investigators will attest to complying with these requirements.

The DRCR.net Procedures Manuals provide details of the imaging procedures.

Retinal images and OCT data will be primary source data, and additional data collected will be directly entered in electronic case report forms, which will be considered the source data.

There is no restriction on the number of participants to be enrolled by a site.

Assessment of adverse events occurring during the Prominent-Eye clinical visit will be obtained through adverse event reporting at the end of each study visit.

A risk-based monitoring approach will be followed, consistent with the FDA “Guidance for Industry Oversight of Clinical Investigations — A Risk-Based Approach to Monitoring” (August 2013).

The risk level for this ancillary research is considered to be no more than minimal risk.

STUDY PARTICIPANT ELIGIBILITY AND ENROLLMENT

2.1 Identifying Eligible Participants and Obtaining Informed Consent

At least 600 participants are expected to be enrolled in this study. Recruitment will continue until the PROMINENT trial has completed enrollment, with up to a maximum of 900 participants enrolling in PROMINENT-Eye. Participants in the PROMINENT trial will be referred to participating DRCR.net sites based on geographic proximity within the U.S. and Canada. The ancillary study brochure providing an overview of the study will be initially discussed with the patient by the PROMINENT investigator and/or coordinator. Interested participants will be provided contact information and encouraged to contact their local PROMINENT-Eye clinical site and (if permitted by the IRB) will consent to having their contact information provided to the local PROMINENT-Eye clinical site and the DRCR.net Coordinating Center. The DRCR.net PROMINENT-Eye clinical site may also contact the participant to facilitate scheduling with participant consent.

At the DRCR.net clinical site, the PROMINENT-Eye study protocol will be discussed with the patient by a DRCR.net study investigator and clinic coordinator. Prior to completing any procedures or collecting any data for this study, informed consent will be obtained. Potential eligibility will be assessed at the screening visit. Patients who are eligible based on the screening visit and Reading Center confirmation of DR severity level will return for additional study imaging visits as outlined below.

2.2 Subject Eligibility and Exclusion Criteria

2.2.1 Eligibility Criteria

- Already randomized at US or Canadian sites in the PROMINENT study
 - a. Enrollment visit into the ancillary study must be conducted within 3 months of randomization into the PROMINENT trial.
- Ability to cooperate with dilated ophthalmic examination and imaging procedures

2.2.2 Study Eye Criteria:

The study participant must have at least one eye meeting all of the inclusion criteria listed below.

The eligibility criteria for a study eye are as follows (both eyes will be considered study eyes if both meet the eligibility criteria at the time of enrollment):

- At least one eye meets the following study eye inclusion criteria:
 - a. ETDRS Diabetic Retinopathy Severity level between 20 and 53 (minimal to severe NPDR), inclusive, on color fundus photographs confirmed by central Reading Center grading.
- Study eye exclusion criteria are:
 - a. Neovascularization present.
 - b. Current central-involved DME based on optical coherence tomography (OCT) central subfield thickness (CST)
 - i. Zeiss Cirrus: $CST \geq 290\mu\text{m}$ in women or $\geq 305\mu\text{m}$ in men
 - ii. Heidelberg Spectralis: $CST \geq 305\mu\text{m}$ in women or $\geq 320\mu\text{m}$ in men
 - c. Known major non-diabetic intraocular pathology that in the opinion of the investigator would substantially and adversely affect visual acuity or lead to ocular neovascularization during the course of the study

- 393 d. Anticipated need for intravitreal anti-VEGF, intravitreal corticosteroid, or PRP in
394 the next 6 months following randomization
395 e. History of intravitreal anti-VEGF or corticosteroid treatment within the prior year
396 for any indication.
397 f. History of intraocular surgery within prior 4 months or anticipated within the next 6
398 months following randomization
399 g. Any history of PRP or vitrectomy
400 h. History of YAG capsulotomy performed within 2 months prior to screening
401 i. Aphakia
402 j. Known substantial media opacities that would preclude successful imaging
403

404 Participants may have 1 or 2 study eyes based on how many eyes meet eligibility criteria.
405

406 **2.3 Screening Evaluation and Baseline Testing**

407 **2.3.1 Ocular Historical Information**

408 An ocular history will be elicited from the potential study participant including prior ocular
409 diseases, surgeries, and treatment.
410

411 **2.3.2 Baseline Testing Procedures**

412 The following procedures will be performed to assess eligibility and/or to serve as baseline
413 measures for the study:

- 414 • The testing procedures are detailed in the DRCR.net Procedures Manuals. Visual acuity
415 testing, ocular exam, fundus photography, and OCT will be performed by DRCR.net
416 certified personnel.
- 417 • The fundus photographs will be sent to a Reading Center for grading.
- 418 • OCT images meeting DRCR.net criteria for manual grading will be sent to a Reading
419 Center.

- 421 1. E-ETDRS visual acuity testing at 3 meters using the Electronic Visual Acuity Tester (including
422 protocol refraction) in each eye
- 423 2. Ocular examination on each eye including dilated ophthalmoscopy
 - 424 • Participant can opt out of ocular exam (dilation will be required regardless)
- 425 3. Spectral Domain OCT using Zeiss Cirrus or Heidelberg Spectralis OCT machine on both eyes
- 426 4. DRCR.net protocol fundus photography in both eyes
 - 427 • The widest field camera type available will be used for color fundus photography.

FOLLOW-UP VISITS

428
429
430
431
432
433
434
435

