3.1 Visit Schedule

Each participant will have protocol specific follow-up visits scheduled at 2 years (\pm 2 months) and at 4 years (\pm 2 months) from the randomization date in the PROMINENT trial. If the PROMINENT study ends prior to a participant's 4-year visit, the participant will have one closeout visit within 3 months of the last PROMINENT visit.

436 Additional retina evaluation visits may occur as required for usual care of the study participant
437 either by the DRCR.net clinical site or by the participant's non-DRCR.net ophthalmologist. If the
438 participant will be examined by a non-DRCR.net ophthalmologist, the participant will be asked to
439 sign a medical records release so any treatment that is documented can be obtained by the
440 DRCR.net site. In addition, participants for whom ocular treatment for DR or DME is planned for
441 the first time during the trial (e.g. anti-VEGF or corticosteroid intravitreal injection, PRP,
442 focal/grid laser, or vitrectomy) will be asked to return to the DRCR.net clinical site to complete the
443 study procedures before the treatment is administered, provided treatment is not urgently needed as
444 determined by the treating physician. If pre-treatment images are not able to be obtained, study
445 images should try to be obtained within 1 month after treatment initiation. Participants who receive
446 treatment will continue follow-up through 4 years.

447
448 Communication between the PROMINENT clinical site and the PROMINENT-Eye clinical site
449 may occur to facilitate compliance with the follow-up schedule if needed.

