6.1 Primary Outcome

The primary outcome is diabetic retinopathy worsening or DME development (composite outcome), based on both eyes for bilateral participants and based on the study eye only for unilateral participants. From a statistical perspective, the primary outcome is a person-level outcome as data from both eyes of bilateral participants is combined into a single outcome measurement. The primary outcome is defined as any of the following:

- For participants with 2 study eyes: 3-step worsening on the ETDRS Retinopathy Severity Scale for Persons (**Table 1**) at a protocol visit. This scale takes into account the retinopathy level of both study eyes.
- For participants with one study eye: 2-step worsening on the ETDRS Retinopathy Severity Scale for Individual Eyes (**Table 2**) in the study eye at a protocol visit. This scale only takes into account the retinopathy level of the study eye.
- Procedure undertaken for the treatment of PDR at any time (even in the absence of photographic documentation) including PRP, intravitreal anti-VEGF, or vitrectomy in at least one study eye.
- Treatment initiated for DME at any time (even in the absence of OCT documentation) including anti-VEGF, corticosteroids, focal/grid laser, or vitrectomy in at least one study eye.
- Development of central-involved DME on OCT with vision loss at the 2-year or 4-year visit. Defined as OCT central subfield thickness above the machine and gender-specific thresholds (see Section 2.2.2 for details) with at least a 10% increase in thickness from baseline and visual acuity 20/32 or worse (letter score ≤ 78) in at least one study eye.

Table 1: Summary of ETDRS Final Retinopathy Severity Scale for Persons

Level in each eye	Description	Scale step
10/10	No DR	1
20/< 20	Microaneurysms only, one eye	2
20/20	Microaneurysms only, both eyes	3
35/< 35	Mild NPDR, one eye	4
35/35	Mild NPDR, both eyes	5
43/< 43	Moderate NPDR, one eye	6
43/43	Moderate NPDR, both eyes	7
47/< 47	Moderately severe NPDR, one eye	8
47/47	Moderately severe NPDR, both eyes	9
53/< 53	Severe or very severe NPDR, one eye	10
53/53	Severe or very severe NPDR, both eyes	11
60 or 61/< 60	Mild PDR and/or PRP, one eye	12
60 or 61/60 or 61	Mild PDR and/or PRP, both eyes	13
65/< 65	Moderate PDR, one eye	14
65/65	Moderate PDR, both eyes	15
71+/< 71	High-risk PDR, one eye	16
71+/71+	High-risk PDR, both eyes	17

587

588
589

Table 2: Summary of ETDRS Final Retinopathy Severity Scale for Individual Eyes

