Level in the eye	Severity	Scale Step
10	DR absent	1
20	Microaneurysms only	2
35	Mild NPDR (hard exudates, soft exudates, and/or mild hemorrhage)	3
43	Moderate NPDR (mild intraretinal microvascular abnormalities or moderate hemorrhage)	4
47	Moderately severe NPDR (mild venous beading, moderate intraretinal microvascular abnormalities or severe hemorrhage)	5
53	Severe or very severe NPDR (moderate/severe venous beading, severe intraretinal microvascular abnormalities and/or very severe hemorrhage)	6
60, 61	Scars of photocoagulation for PDR (60) or mild PDR (61)	7
65	Moderate PDR	8
71, 75	High-Risk PDR	9
81, 85	High-Risk PDR with vitreous hemorrhage	10

590

591 **6.2 Sample Size Estimation**

592 Based on data from eyes with baseline retinopathy in the ACCORD study, it is anticipated that
 593 approximately 50% of PROMINENT study participants will have minimal to severe NPDR (levels
 594 20-53) in at least one eye. Among participants with minimal to severe NPDR in at least one eye,
 595 the percentage of patients with either a 3-step patient-level progression or photocoagulation was
 596 approximately 5% in the fenofibrate group and 12% in the placebo group. For the entire ACCORD
 597 cohort (i.e. with and without baseline retinopathy), the rate of DME worsening on color
 598 photographs was approximately 3% over 4 years in both the fenofibrate and control groups.
 599 However, the percentage of patients with baseline retinopathy and worsening DME without
 600 worsening retinopathy is not reported. In addition, DME progression in ACCORD was assessed by
 601 color photographs while in the current study it will be assessed by OCT, which has been shown to
 602 be more sensitive at detecting DME.³² Therefore, it is unknown what impact the primary outcome
 603 components, besides retinopathy progression, will have on the projected outcome, resulting in
 604 uncertainty around these estimates.

605

606 The table below shows the required sample size for 80% power with a type I error rate of 5% and a
 607 null hypothesis of no difference between groups (two-tailed test) for a time-to-event outcome (log-
 608 rank test). These calculations were based on the 4-year outcome rate in the placebo group and the
 609 resulting hazard ratio when comparing the outcome rate in the pemafibrate group. The outcome
 610 times are assumed to follow an exponential distribution and the estimates include adjustment for

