643 to produce confounding. However, the presence of confounding will be evaluated in regression
644 models by including factors potentially associated with the outcome for which there is an imbalance
645 between groups.
646

647 **6.3.3 Per Protocol Analyses**

648 Per protocol analyses mimicking the primary intention-to-treat analyses will be performed on the
649 following cohorts:
650

- 651 • Participants with no major protocol deviations as defined by the PROMINENT trial.
 - 652 • Participants with $\geq 80\%$ compliance during the treatment period as defined by the
653 PROMINENT trial.
- 654

655 **6.3.4 Sensitivity Analyses**

656 The following sensitivity analyses will be conducted:
657

- 658 • Repeat the primary analysis while censoring data from participants who receive treatment
659 for DME when the OCT central subfield thickness in the treated eye did not meet the
660 outcome criteria for DME with vision loss when the treatment was given. Participants who
661 do not have an OCT scan from the visit at which treatment is given also will be censored in
662 this analysis.
663

664 **6.3.5 Subgroup Analyses**

665 The treatment effect in subgroups defined by baseline factors will be assessed in pre-planned
666 subgroup analyses. These analyses will be conducted to determine whether the treatment effect in
667 any subgroup differs from the overall treatment effect. The study is not expected to have sufficient
668 statistical power for definitive conclusions in subgroups and statistical power will be low to
669 formally test for the presence of subgroup effects. Interpretation of subgroup analyses will depend
670 on whether the overall analysis demonstrates a significant treatment effect. In the absence of a
671 significant treatment effect in the primary analysis, assessment of subgroups will be considered
672 exploratory and used to suggest hypotheses for further investigation in future studies.

673
674 The general approach for these analyses will be to add an interaction term for the subgroup factor
675 by treatment group into the proportional hazards model used for the primary analysis.

676
677 The planned subgroups for analyses are as follows:

- 678 • Baseline person-level retinopathy level: Steps 2-4, Steps 5-6, Steps 7-9, and Steps 10-11

679
680 Statistical analyses will only be conducted for a subgroup if there are at least 20 participants in each

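### Focal/grid laser for DME is a primary event but is missing from the anticipated-treatment exclusion, so laser already expected at entry can dilute the hazard ratio

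*Combined protocol and SAP*

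**What the plan says.** **Endpoint.** Sections 1.8 F and 6.1 make any treatment started for DME a primary event, at any time and with no OCT needed, "including anti-VEGF, corticosteroids, focal/grid laser, or vitrectomy in at least one study eye".

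**Exclusions in section 2.2.2:**
- Exclusion d: "Anticipated need for intravitreal anti-VEGF, intravitreal corticosteroid, or PRP in" the 6 months after randomization. Section 1.8 B repeats it. Neither place names focal/grid laser.
- Exclusion f: "History of intraocular surgery within prior 4 months or anticipated within the next 6" months. This reaches a planned vitrectomy.
- Exclusion h: "History of YAG capsulotomy performed within 2 months prior to screening". A laser procedure thus has its own line and is not treated as part of intraocular surgery.
- Exclusion b: central-involved DME, defined by OCT central subfield thickness at or above machine- and sex-specific limits. Eyes with DME below those limits stay eligible.

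**Elsewhere.** Sections 3.1 and 5.1 name focal/grid laser next to anti-VEGF, corticosteroid, PRP and vitrectomy as a first treatment that should prompt study imaging.

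**Sensitivity analysis (6.3.4).** "Repeat the primary analysis while censoring data from participants who receive treatment" for DME when thickness in the treated eye did not meet the outcome criteria for DME with vision loss. Participants with no OCT from the treatment visit are censored too.

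**The concern.** Exclusions d and f appear meant to keep out eyes about to receive a treatment that would itself be an endpoint event. Focal/grid laser is a named event-defining treatment that this screen misses, and no reason is given.

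The OCT component of the endpoint guards against disease already present, because it requires at least a 10% rise in thickness from baseline. The treatment component has no such guard. An eye with non-central DME and laser expected at enrolment can enter, be lasered and count as DME development, although the decision mostly reflects its state at entry.

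Such events would be expected about equally in both arms. They would pull the composite hazard ratio toward 1 and do the same to the DME secondary outcomes, which count the same treatments. Section 6.2 argues that treatment-related and DME-related events can only help power and calls its estimates conservative. That holds only for events that respond to the drug.

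**Working it through.** **Inputs (section 6.2).** "required sample size for 80% power with a type I error rate of 5% and a" two-sided log-rank test; 4-year event rates of 12% (placebo) and 5% (pemafibrate); 15% attrition over 4 years; exponential event and attrition times; 600 participants, with a cap of 900 from section 1.8 C. Equal allocation is assumed.

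**Step 1: reproduce the plan's figure.**
- Hazard ratio: ln(0.95)/ln(0.88) = 0.401, which the plan rounds to 0.4.
- Events needed (Freedman): (1.960 + 0.842)² × (1.4/0.6)² = 7.849 × 5.444 = 42.7.
- Probability of an observed event: λ/(λ+γ) × [1 − exp(−4(λ+γ))], with γ = −ln(0.85)/4 = 0.0406 per year. At hazard ratio 0.40 the mean over arms is 0.0785.
- N = 42.7/0.0785 ≈ 544, or 546 rounded up to equal arms. Table 3 gives 536, a difference of 1.9%. All 15 cells of Table 3 reproduce within 3%.

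**Step 2: add events that do not respond to the drug.** Let a share x of each arm enter with laser already anticipated and have the event whichever arm they are in. The documents do not give x, so the values below are assumptions.
- 4-year rates: 1 − (1−x)(0.88) for placebo and 1 − (1−x)(0.95) for pemafibrate.
- Hazard ratio: the ratio of log survival at 4 years.
- Power: Φ(√d × (1−HR)/(1+HR) − 1.960), where d is the expected number of observed events.

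Worked case, x = 1% (6 of 600):
- Rates: 1 − 0.99 × 0.88 = 12.88% and 1 − 0.99 × 0.95 = 5.95%.
- HR = ln(0.9405)/ln(0.8712) = 0.445.
- Observed-event probabilities are 0.1191 and 0.0550, so d = 600 × 0.0870 = 52.2.
- √52.2 × 0.555/1.445 = 2.78, and Φ(2.78 − 1.96) = 79%.

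| x | Placebo | Pemafibrate | HR | Events, N=600 | Power, N=600 | Power, N=900 |
|---|---|---|---|---|---|---|
| 0 | 12.00% | 5.00% | 0.40 | 47.1 | 83.5% | 95% |
| 0.5% | 12.44% | 5.48% | 0.42 | 49.7 | 81% | 94% |
| 1% | 12.88% | 5.95% | 0.445 | 52.2 | 79% | 93% |
| 2% | 13.76% | 6.90% | 0.48 | 57.3 | 75% | 90% |
| 3% | 14.64% | 7.85% | 0.52 | 62.4 | 71% | 87% |

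**Step 3: check.** If the planned-laser events are taken as not subject to attrition, power at 600 is 80%, 76% and 72% for x = 1%, 2% and 3%. A log-rank simulation with laser spread over the first 6 months (8,000 runs per setting) gives 80%, 76% and 70%. The conclusion does not depend on the method.

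In every row the placebo rate rises while power falls, the opposite of what section 6.2 expects from a higher event rate.

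**The case against.** **The sensitivity analysis already covers this.** Laser for non-central DME below the thickness limits is what section 6.3.4 censors, so the influence of such events would be visible. This stands and lowers the priority. It does not change the primary test, and because it also censors other DME treatments it does not isolate this problem.

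**The number may be negligible.** The eye must be below the thickness limits, have laser anticipated, and have no anti-VEGF, corticosteroid or PRP anticipated. No rate is given. A reader might infer that a few percent is likely from the macular edema rows of the ACCORD Eye table in the introduction (5.3% + 1.5% + 0.8% = 7.6%). The documents do not support that: the table is broken in extraction, covers the whole cohort, does not separate central from non-central edema, and says nothing about planned laser.

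**The 12% and 5% may already include some laser.** Section 6.2 describes them first as progression or photocoagulation, of unstated type, and later as progression on photographs only. If focal laser was included, part of the dilution is already in the 0.40. This stands as an uncertainty.

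**The drug may have had some chance to act.** A reader might infer that these events were beyond prevention. Enrolment may come up to 3 months after randomization in the parent trial, so that is too strong; driven mainly by disease at entry is what can be said.

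**Laser is not the only mismatch.** Exclusion d limits corticosteroid to the intravitreal route and the event list does not. This is correct on the text, so laser should not be called the sole omission.

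**Conclusion.** The mismatch is real, and no other exclusion clearly closes it. Its consequence is dilution and lost power, provided anticipated laser is balanced between arms; it is not a source of false-positive bias.

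The size is unknown and could be near zero. At an assumed 1% the calculated power at 600 drops just below 80%; at an assumed 3% it is 71%. With 900 participants, power stays at 87% or above across the range shown. These figures rest on the plan's 12% and 5% rates, equal allocation, and events wholly unresponsive to treatment.

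With the planned sensitivity analysis in place, this is a wording gap worth closing and not a threat to the trial's validity.

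**What to change.** Reconcile exclusion d in sections 1.8 B and 2.2.2 with the DME-treatment event list in sections 1.8 F and 6.1 by adding anticipated focal/grid laser. This takes one phrase in each place; the cost is that a few otherwise eligible eyes are excluded.

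For eyes already enrolled, leave the primary endpoint unchanged and rely on the section 6.3.4 sensitivity analysis. A rule that discounts laser planned at enrolment would alter the primary endpoint. It would also need a record of planned laser that the documents do not describe: the baseline history covers past disease, surgery and treatment, and the eye examination can be declined.

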3.1 Visit Schedule

Each participant will have protocol specific follow-up visits scheduled at 2 years (\pm 2 months) and at 4 years (\pm 2 months) from the randomization date in the PROMINENT trial. If the PROMINENT study ends prior to a participant's 4-year visit, the participant will have one closeout visit within 3 months of the last PROMINENT visit.

436 Additional retina evaluation visits may occur as required for usual care of the study participant
437 either by the DRCR.net clinical site or by the participant's non-DRCR.net ophthalmologist. If the
438 participant will be examined by a non-DRCR.net ophthalmologist, the participant will be asked to
439 sign a medical records release so any treatment that is documented can be obtained by the
440 DRCR.net site. In addition, participants for whom ocular treatment for DR or DME is planned for
441 the first time during the trial (e.g. anti-VEGF or corticosteroid intravitreal injection, PRP,
442 focal/grid laser, or vitrectomy) will be asked to return to the DRCR.net clinical site to complete the
443 study procedures before the treatment is administered, provided treatment is not urgently needed as
444 determined by the treating physician. If pre-treatment images are not able to be obtained, study
445 images should try to be obtained within 1 month after treatment initiation. Participants who receive
446 treatment will continue follow-up through 4 years.

447
448 Communication between the PROMINENT clinical site and the PROMINENT-Eye clinical site
449 may occur to facilitate compliance with the follow-up schedule if needed.

